9.0 Efficacy Analysis

9.1 General Considerations

All analyses in this session will be presented for the 3 treatment groups: venetoclax in combination with either azacitidine or decitabine, and all treated subjects combined.

9.1.1**Analysis of Efficacy Endpoints by Variable Type**

The primary endpoint is composite complete remission (CR + CRi), a complete remission (CR) with or without complete hematologic recovery (CRi). The secondary endpoints are rates of complete remission (CR), complete remission with incomplete hematologic recovery (CRi), and transfusion-independence rates for red blood cells and platelets separately and combined. The observed rates for each endpoint will be presented with a 95% confidence interval. Rates of composite complete remission (CR + CRi) in molecular subtypes will be similarly presented.

Time to the first absolute neutrophil count improvement and hemoglobin improvement as well as duration of the first absolute neutrophil count improvement and hemoglobin improvement will also be analyzed using Kaplan-Meier curve, where median time to improvement and duration of improvement with their corresponding 95% CI will be provided.

9.1.2**Missing Data Imputation for Efficacy Endpoints**

Subjects who do not have any post-baseline IWG assessments will be considered as non-responders in the remission rate analyses.

9.2**Primary Efficacy Analysis**

The primary endpoint is the composite complete remission rate (CR + CRi) as identified by the investigators during the study. An exact 95% confidence interval based on the binomial distribution will be provided along with the rate.

9.3**Secondary Efficacy Analyses****9.3.1****Remissions**

Rates of complete remission and complete remission with incomplete hematologic recovery (as the best response) as identified by the investigator will be tabulated separately. Exact 95% confidence intervals will also be provided.

9.3.2 Transfusion Independence

Post baseline transfusion independence rate will be calculated as the proportion of subjects who achieved transfusion independence post baseline regardless of their baseline transfusion status. Transfusion independence is defined as a period of at least 56 days (\geq 56 days) with no transfusion after the first dose of study drug and on or before the last dose of study drug + 30 days, relapse, death, or before the initiation of post-treatment therapy, whichever is earliest. The transfusion independence rate will be evaluated for 1) red blood cells (RBC), 2) platelets, and 3) RBC and platelets. Exact 95% confidence intervals will also be provided.

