### 3.3 Secondary Endpoints

---

The secondary endpoints are:

- Overall Response Rates (CR, CRi): complete remission (CR) or complete remission with incomplete hematologic recovery (CRi) as described by the modified IWG criteria.
- Transfusion Independence: evaluate the rate of RBC and platelet transfusion dependence (defined as having received  $\geq 2$  units of RBCs and/or platelets within 56 days prior to study) at baseline and assess transfusion independence, defined as at least 56 consecutive days without a RBC or platelet transfusion during the treatment period.

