### 30-Day Safety Follow-Up:\*

 INTERVIEW	

• Adverse event assessment

• ECOG Performance status

	

• Prior/concomitant therapy

 EXAM	

• Vital signs

• Post-treatment follow-up

	

• Physical examination

 LAB	

• Clinical chemistry, hematology, and coagulation

	

**NOTES:** \* This visit is to be performed for all subjects 30 days ( $\pm$  2 days) after their last dose of study drug.

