### 3.18 Subject Withdrawal from Study

All attempts must be made to determine the date of the last study drug dose and the primary reason for discontinuation of study drug or study participation. The information will be recorded on the appropriate eCRF page. If a subject discontinues study participation, the procedures outlined for the Final Visit should be completed as soon as possible, preferably within 2 weeks. A 30-day safety follow-up visit will also be conducted after the last dose of study drug. If the subject refuses or is unable to attend the safety follow-up visit, this should be noted in the subject's source documentation.

However, these procedures should not interfere with the initiation of any new treatments or therapeutic modalities that the investigator feels are necessary to treat the subject's condition. Following discontinuation of study drug, the subject will be treated in accordance with the investigator's best clinical judgment, irrespective of whether or not the subject decides to continue participation in the

study. Post-treatment follow-up (i.e., all cancer therapies including stem cell transplantation, regimens, dates of initiation and completion, etc.) will be collected at the 30-day safety follow-up visit.

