4.3.2 Secondary Efficacy Endpoints

The secondary endpoints are:

- Response of CR or CRi: complete remission (CR) or complete remission with incomplete hematologic recovery (CRi) as described by the modified IWG criteria.

- Transfusion independence rate is defined as the proportion of subjects who achieved post-baseline transfusion independence, which is defined as a period of at least 56 days with no transfusion after the first dose of study drug and within 30 days of the last dose of study drug, death, initiation of post-treatment therapy, whichever is earliest. Transfusion independence rate will be calculated for both RBC transfusion and platelet transfusion separately and together.

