5.0 Analysis Populations

5.1 Definition of Analysis Populations

Subjects who receive at least one dose of venetoclax, azacitidine, or decitabine will be included in all analyses unless specified otherwise.

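### The SAP's transfusion-independence window does not stop when observation stops, so a subject who leaves early can be counted as independent on as few as about 26 observed days

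*SAP*

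**What the plan says.** SAP 9.3.2 counts a subject as transfusion-independent after a run of 56 or more days "with no transfusion after the first dose of study drug and on or before the last dose of study drug + 30 days". The sentence then lists the other dates that can close the window: "relapse, death, or before the initiation of post-treatment therapy, whichever is earliest". SAP 4.3.2 words the endpoint this way: "a period of at least 56 days with no transfusion after the first dose of study drug and within 30 days of the last dose". It adds death and post-treatment therapy as further ends. It does not list relapse.

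Last contact, withdrawal of consent and loss to follow-up appear in neither list. Neither section says that the 56 days must be observed.

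Other provisions that bear on this:

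- **Denominator (SAP 5.1):** "Subjects who receive at least one dose of venetoclax, azacitidine, or decitabine will be included in all analyses", barring stated exceptions. Dropouts therefore stay in and must be scored.
- **Missing data (SAP 9.1.2):** the only efficacy rule is "Subjects who do not have any post-baseline IWG assessments will be considered as non-responders in the remission rate analyses". It does not reach transfusion independence.
- **Protocol 3.3:** independence is "at least 56 consecutive days without a RBC or platelet transfusion during the treatment period", with no 30-day extension.
- **Planned follow-up:** Operations Manual 3.3 has concomitant medication recorded until 30 days after the last dose. Operations Manual 2.2 says of the safety visit: "This visit is to be performed for all subjects 30 days" (± 2 days) after the last dose.
- **Early exit:** Protocol 5.5 and 5.6 allow for loss to follow-up and withdrawal of consent. Operations Manual 3.18 says what to document "If the subject refuses or is unable to attend the safety follow-up visit".

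**The concern.** The endpoint is met when no transfusion record falls between two dates. After a subject leaves the study no records can arise, so a program that follows the SAP's list of window ends finds none and returns a success. The listed ends give little protection here, because relapse, death or new therapy after last contact may also go unseen. Under Operations Manual 3.17, post-treatment therapy is collected at the same 30-day visit that such a subject misses.

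At stake is a secondary endpoint in a single-arm study. Compared with a count of observed days only, unobserved credit can move a subject from not independent to independent and never the reverse, and there is no control arm with the same handling to set against it.

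**Working it through.** The plan states no target or precision for transfusion independence. Its only design figure is the 13% precision for the CR + CRi rate. The Wald formula reproduces it: 1.96 × √(0.5 × 0.5 / 60) = 12.65 points at a rate of 50%. The point made here does not depend on that figure; it only gives a sense of scale.

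**Inputs.** Run length 56 days and extension 30 days (SAP 9.3.2 and 4.3.2); N = 60 (SAP 4.4). The dropout rate is not given. Last contact is assumed not to precede the last recorded dose.

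**1. Unobserved share.** Let last contact fall c days after the last dose, with c from 0 to 30, and let the qualifying run end at last dose + 30.

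- Unobserved days = 30 − c
- Observed days needed = 56 − (30 − c) = 26 + c
- At c = 0: 30 / 56 = 54% unobserved and 26 observed days suffice
- At c = 30 (follow-up completed): 0 unobserved and 56 observed

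**2. Worked example.** Last transfusion on Day 40; last dose and withdrawal of consent on Day 66.

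- The window runs from Day 41 to Day 66 + 30 = Day 96
- Length: 96 − 41 + 1 = 56 days, so the definition is met
- Observed: 66 − 41 + 1 = 26 days

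**3. Earliest last dose that can qualify.** Take a subject with no recorded transfusion who is lost on the day of the last dose L. The count starts on day s, which is Day 1 or Day 2 depending on how *after the first dose* is read.

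- As written: (L + 30) − s + 1 ≥ 56, so L ≥ 25 + s, which is Day 26 or Day 27
- Window ended at last contact: L − s + 1 ≥ 56, so L ≥ 55 + s, which is Day 56 or Day 57

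A last dose on Cycle 1 Day 28 gives a window to Day 58. That is 58 or 57 days, so the subject qualifies on 28 or 27 observed days.

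**4. Effect on the rate.** One subject is 1 / 60 = 1.67 points. The counts below are illustrations, starting from an assumed 30 of 60, with exact 95% intervals:

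| Reclassified subjects | Rate | Exact 95% CI |
|---|---|---|
| 0 | 50.0% | 36.8 to 63.2 |
| 1 | 51.7% | 38.4 to 64.8 |
| 3 | 55.0% | 41.6 to 67.9 |
| 6 | 60.0% | 46.5 to 72.4 |

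The SAP also reports the azacitidine and decitabine groups separately. Their denominators are smaller, so one subject moves those rates by more.

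**The case against.** The strongest reply is that the SAP is silent rather than wrong. It never states that unobserved days are transfusion-free, and a 56-day period without transfusion could be read as 56 documented days. The 30-day extension also matches planned collection: medication recording and a visit for all subjects run to that point, subjects who stop drug early are to stay on schedule, and calls and a certified letter are required before anyone is declared lost. The affected group is narrow. Such a subject has no earlier 56-day run, leaves before the 30-day point with 26 to 55 observed transfusion-free days, and has no known relapse, death or new therapy that closes the window too soon. No test or success threshold depends on this endpoint.

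All of this is fair, and it limits the point to subjects who leave early. It does not close the gap. The list of window ends reads as complete, every dosed subject must be scored, and no rule says how to score one whose records stop.

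Three stronger readings are tempting, and the documents do not support them:

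- **That missing data count as failure for remission and as success here.** SAP 9.1.2 makes non-responders only of subjects with no post-baseline response assessment at all. A subject with a documented CR or CRi who then drops out remains a responder.
- **That the Operations Manual expects missed 30-day visits.** Section 3.18 provides for that contingency and also says that the visit will take place.
- **That the rate is overstated by 5 or 10 points.** Those figures follow from assumed counts of 3 or 6 subjects. They also measure reclassification, not bias, since some of these subjects may truly have gone 56 days without a transfusion.

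**Conclusion.** The point holds for subjects whose observation ends before last dose + 30 days. It does not hold for those who complete follow-up, apart from the visit's 2-day tolerance. In the affected group, the rule applied literally credits up to 30 of the 56 days without data, and the reported rate can only go up as a result. The credit also departs from Protocol 3.3: the Operations Manual classes the 30-day visit as post-treatment, so the extra 30 days come from the SAP alone.

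The conclusion rests on a literal reading of the list of window ends, which is the natural reading for programming. How far the rate would move cannot be computed, because no dropout rate is given. Only the effect per subject, 1.7 points at N = 60, is firm. The matter should be settled in the SAP before database lock, but it does not touch the primary endpoint.

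**What to change.** In SAP 4.3.2 and 9.3.2:

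1. Add the last date on which transfusion data were collected (last study contact) to the dates that end the window.
2. State that subjects without 56 observed consecutive transfusion-free days count as not independent.
3. Give both sections the same list of ends, since relapse now appears in only one, and align that list with Protocol 3.3 on whether days after the treatment period count.

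The cost is one phrase and one counting rule in two sections, with no new data. The downside is that the rule is conservative: some dropouts who would have reached 56 days will count as failures, and the reported rate may fall slightly. If the sponsor already intends to stop at last contact, writing it down changes no result.

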## 5.6 Follow-Up for Subject Withdrawal from Study

---

To minimize missing data for effectiveness and safety assessments, subjects who prematurely discontinue study drug treatment should continue to be followed for all regularly scheduled visits, unless subjects have decided to discontinue the study participation entirely (withdrawal of informed consent). Subjects should be advised on the continued scientific importance of their data even if they discontinue treatment with study drug early.

If a subject prematurely discontinues study participation, the procedures outlined for the Final Visit should be completed as soon as possible, preferably within 2 weeks. In addition, if a subject is willing, a 30-day follow-up visit after the last dose of study drug should be completed to capture all treatment-emergent adverse events/serious adverse events have been resolved to  $\leq$  Grade 1, baseline level, or initiation of a new treatment, whichever is earlier, or, in the opinion of the investigator, the event is unlikely to resolve.

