### 2.1 Individual Treatment Period Visit Activities

---

This section presents a list of activities performed during each visit, organized by visit. The dot pattern on the upper right indicates the place of the visit in the overall Treatment Period Activity Schedule.

Activities are grouped by category (Interview, Exam, etc.). Further information about each activity is provided in Section 3.

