## 3.15 Bone Marrow Aspirate and/or Biopsy

---

Bone marrow aspirate will be performed at time points described in Section 2.1. Bone marrow aspirates performed throughout the study should be captured on an eCRF, including those performed to confirm or rule out disease progression. Bone marrow will be assessed at:

- Screening
- the end of Cycle 1 (must be performed within  $\pm 3$  days of Cycle 1 Day 28 and resulted prior to the administration of treatment for Cycle 2),
- the end of Cycle 2 (must be performed within  $\pm 3$  days of Cycle 2 Day 28 and resulted prior to administration of treatment for Cycle 3) [only if complete remission (CR)/complete remission with incomplete blood count recovery (CRI) not achieved at end of Cycle 1],
- the end of Cycle 4 (must be performed within  $\pm 3$  days of Cycle 4 Day 28 and resulted prior to administration of treatment for Cycle 5) [only if CR/CRI not achieved at end of Cycle 2], and
- upon concern for relapse, and

- the Final Visit/end of Cycle 6 (must be performed within  $\pm$  3 days of Cycle 6 Day 28).

Historical bone marrow aspirates and biopsies assessed locally to confirm the diagnosis can be used as baseline assessments to satisfy eligibility criteria and for screening as long as the samples were taken 30 days prior to first study drug administration. Bone marrow aspirates and/or biopsies performed in addition to those required per protocol, as standard of care throughout the study as per institutional practice, should also be captured on an eCRF.

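### SAP 4.3.2 and 9.3.2 close the transfusion-independence window at different points (only 9.3.2 stops at relapse), and the pooled rate cannot show how many baseline-dependent subjects became independent

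*SAP*

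**What the plan says.** SAP 4.3.2, the endpoint definition, asks for a 56-day transfusion-free stretch that starts after dosing begins and lies "within 30 days of the last dose of study drug, death, initiation of post-treatment therapy, whichever is earliest". SAP 9.3.2, the analysis section, asks for the same stretch "on or before the last dose of study drug + 30 days, relapse, death, or before the initiation of post-treatment therapy, whichever is earliest". The second list contains relapse and the first does not. Both are current text and both define the same endpoint, for red cells, platelets and the two together.

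Protocol 3.3 words independence a third way: "defined as at least 56 consecutive days without a RBC or platelet transfusion during the treatment period". It gives no extension beyond the last dose and names no event that closes the period. The same bullet pairs independence with baseline dependence, which it sets at two or more "units of RBCs and/or platelets within 56 days prior to study".

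On the denominator, SAP 9.3.2 says: "Post baseline transfusion independence rate will be calculated as the proportion of subjects who achieved transfusion independence post baseline regardless of their baseline transfusion status". SAP 7.1 tabulates baseline red-cell and platelet dependence as separate yes/no counts. The subgroup analyses in SAP 9.5 apply to CR + CRi only. No current section crosses baseline dependence with later independence.

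**The concern.** Whether a subject counts as a success can depend on which SAP section the programmer follows. 9.3.2 is the analysis section and would probably be used, but the reported rate would then not match the endpoint as SAP 4.3.2 lists it, and a reader of the report could not tell which window applied. The protocol's wording adds a third candidate.

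A separate matter is what the rate can tell anyone. It mixes subjects who stopped needing transfusions with subjects who never needed them. With no control arm to compare against, the pooled figure cannot separate the two groups, although protocol 3.3 names baseline dependence and on-study independence together.

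**Working it through.** The plan states no figure for this endpoint, so there is none to reproduce.

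**Notation.** T = day of last transfusion, R = day of relapse, L = day of last dose, with Day 1 the first dose (SAP 6.4). Free days run from T + 1 to the day the window closes. I read SAP 4.3.2 as closing at the earliest of L + 30, death or new therapy, and SAP 9.3.2 as closing at the earliest of those or R.

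**Conditions for success** when relapse comes before the other closing events:
- 4.3.2: (L + 30) − T ≥ 56
- 9.3.2: R − T ≥ 56

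**Example.** T = 40, R = 85, L = 66 or later, no transfusion through Day 96, and no death or new therapy by then.
- 4.3.2: 96 − 40 = 56 free days, a success.
- 9.3.2: 85 − 40 = 45 free days, a failure.

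No earlier 56-day gap can rescue this subject, because only 40 − 1 = 39 days separate Day 1 and Day 40. Dosing past relapse is not needed either: L = 66 already gives a window end of 66 + 30 = 96.

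**General band.** With L = R, 4.3.2 needs R − T ≥ 56 − 30 = 26 and 9.3.2 needs R − T ≥ 56. The texts can disagree for R − T from 26 to 55, which is 30 possible values. With L = R + 10 the band is 16 to 55, or 40 values.

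**Effect on the rate (assumed counts).** The documents give no relapse or transfusion frequencies. Suppose 30 of 60 succeed under 4.3.2 (50.0%). If 1, 3 or 6 of them complete the 56 days only with time after relapse, 9.3.2 gives 29/60 = 48.3%, 27/60 = 45.0% or 24/60 = 40.0%.

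**Protocol wording.** Operations Manual 2.2 places the 30-day safety visit in the post-treatment period. Operations Manual 6.1 couples the end of the treatment period with the final visit, and protocol 4.1 sets that visit at treatment discontinuation or the end of Cycle 6. On that reading the protocol's period stops around L, while the SAP allows up to L + 30.

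**What the pooled rate leaves open (assumed counts).** With D of 60 subjects dependent at baseline and S successes overall, the number k of dependent subjects who became independent satisfies max(0, S − (60 − D)) ≤ k ≤ min(D, S). For S = 36 (60%):

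| D | k | conversion k/D |
|---|---|---|
| 18 | 0 to 18 | 0% to 100% |
| 30 | 6 to 30 | 20% to 100% |
| 42 | 18 to 36 | 43% to 86% |

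If D = 30 and 24 or 27 of the 30 non-dependent subjects stay independent (80% or 90%), then k = 36 − 24 = 12 (40%) or 36 − 27 = 9 (30%), well below the pooled 60%.

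**Precision of a conversion rate** (exact Clopper-Pearson 95% interval at an observed 50%):
- 9/18: 26.0% to 74.0%, half-width about 24 points
- 15/30: 31.3% to 68.7%, about 19 points
- 21/42: 34.2% to 65.8%, about 16 points
- 30/60, for comparison: 36.8% to 63.2%, about 13 points

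**The case against.** The window mismatch needs an unusual subject: one who relapses, survives, starts no new therapy, stays transfusion-free beyond relapse and has no earlier 56-day gap. Protocol 5.5 continues treatment until documented progression, and protocol 4.1 allows dosing beyond it only with continuing benefit and discussion with the medical monitor, so the wider band is the exception. SAP 9.3.2 also states a definition of its own, so a result programmed from it does match one SAP definition. All of this stands and limits the size. It does not justify leaving two definitions of one endpoint in the same document.

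Several stronger readings are tempting, and the documents do not support them:

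- **That relapse is undefined, so 9.3.2 cannot be applied.** Operations Manual 3.15 calls for marrow assessment "upon concern for relapse", and Table 2 has no relapse category. But Operations Manual 3.16 bases disease assessment on the cited IWG guideline, which may supply the criterion. What can be shown is a missing cross-reference in the SAP.
- **That the protocol's period might run well past the last dose.** Protocol 5.6 says "subjects who prematurely discontinue study drug treatment should continue to be followed for all regularly scheduled visits", and Operations Manual 2.1 describes its visit list as showing "the place of the visit in the overall Treatment Period Activity Schedule". The placement of the 30-day visit under the post-treatment period and the wording of Operations Manual 6.1 favour the shorter reading. The term is not defined outright, so I put no number on a longer one.
- **That omitting a conversion rate departs from the protocol.** Protocol 3.3 asks that baseline dependence be evaluated and independence assessed, and SAP 7.1 and 9.3.2 do both. No current passage promises a conversion rate. The SAP's change summary mentions one, but such a summary describes superseded text and carries no weight here.

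The dependent counts and maintenance rates above are assumptions. They show what the pooled rate cannot resolve, and they are no evidence about this trial.

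**Conclusion.** The contradiction within the SAP holds: only 9.3.2 closes the 56-day window at relapse, and a subject can succeed under one text and fail under the other. The 26-to-55-day band is an outer bound that assumes the last dose on the day of relapse. The number of subjects affected cannot be derived from the documents and is probably small. The protocol's wording most naturally excludes the SAP's tail of up to 30 days, and the SAP does not say how the two relate.

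The missing breakdown by baseline status is an improvement to the plan, not an error in it. It is worthwhile because the pooled rate in a single-arm study can be compatible with a very wide range of conversion rates.

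Both matters concern a descriptive secondary endpoint. Neither affects the primary CR + CRi analysis or the sample size.

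**What to change.** **Window.** Use the 9.3.2 window, including relapse, in both SAP 4.3.2 and SAP 9.3.2. Point to the criterion by which relapse is judged. Add a sentence stating how this window relates to the treatment period named in protocol 3.3.

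**Baseline status.** Keep the pooled rate. Add, with exact 95% confidence intervals, for red cells, platelets and both:
- the conversion rate: baseline-dependent subjects who reach 56 transfusion-free days, divided by all baseline-dependent subjects;
- the maintenance rate: the same proportion among baseline-independent subjects.

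State how the protocol's two-unit threshold applies to each product. SAP 7.1 classifies red-cell and platelet dependence separately, and one unit of each could meet a combined count but neither single-product count.

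**Cost.** SAP wording and a few table rows. Protocol 7.3 leaves analysis detail to the SAP, and protocol 7.1 has the SAP finalized before database lock, so the change belongs before then. The price is smaller denominators: half-widths of about 24, 19 or 16 points for an assumed 18, 30 or 42 dependent subjects. The new rates should be presented as descriptive.
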